treatment in patients with chronic rhinitis

Study device: ClariFix® Cryotherapy device

Study design: A prospective, multicenter, randomized, sham-controlled, single-blinded study

Enrollment: A total of 128 research participants randomized 1:1 to active treatment or sham

control

Treatment: 1. Active: treatment with the ClariFix® device

2. Control: sham procedure with a ClariFix device minus the cryogen

cannister

Clinical centers: Up to 12 US investigational centers

Inclusion Participants MUST:

criteria: 1. Be ≥ 21 years of age.

- 2. Has been diagnosed with chronic nonallergic or allergic rhinitis.
- 3. Have moderate to severe symptoms of rhinorrhea (individual reflective Total Nasal Symptoms Score [rTNSS] symptom rating of 2 or 3), mild to severe symptoms of nasal congestion (individual rTNSS symptom rating of 1, 2, or 3), and a minimum total rTNSS of 4 (out of 12) at baseline.
- 4. Have an allergy test (by skin prick or intradermal testing or by validated *in vitro* tests for specific Immunoglobin E [IgE]) on file within 12 months of the baseline visit.
- 5. Be an appropriate candidate for bilateral ClariFix treatment performed under local anesthesia.

6. Be willing and able to comply with all study elements, as indicated by their written informed consent.

Exclusion criteria:

Participants MUST NOT:

- 1. Have clinically significant anatomic obstructions that in the investigator's opinion limit access to the posterior nose, including but not limited to severe septal deviation or perforation, nasal polyps, and/or sinonasal tumor.
- 2. Have had previous sinus or nasal surgery within 6 months of study enrollment.
- 3. Have previously undergone cryotherapy or other surgical interventions for rhinitis.
- 4. Have an active nasal or sinus infection.
- 5. Have rhinitis symptoms that are primarily due to seasonal allergies.
- 6. Have plans to (or otherwise anticipates the need to) undergo an ENT procedure concurrently or within 3 months after the study procedure.
- 7. Is on prescribed anticoagulants (eg, warfarin, Plavix) or 325 mg aspirin that cannot be discontinued before the procedure (81 mg aspirin and herbal supplements are acceptable).
- 8. Be unable to discontinue ipratropium bromide (IB) at least 14 days before baseline and through the 90-day follow-up visit.
- 9. Have a history of chronic epistaxis or experienced a significant epistaxis event (defined as epistaxis requiring medical intervention) in the past 3 months.
- 10. Have a history of rhinitis medicamentosa.
- 11. Have had previous head and/or neck irradiation.
- 12. Have an allergy or intolerance to local anesthetic agents.
- 13. Have cryoglobulinemia, paroxysmal cold hemoglobinuria, cold urticaria, Raynaud's disease, and/or open and/or infected wounds at or near the target tissue.
- 14. Have a neurological, medical, psychiatric condition, or social circumstance that would potentially increase risk, interfere with study participation, or confound interpretation of study data.
- 15. Be participating in another clinical research study.

Objective:

To demonstrate the superiority of treatment with the ClariFix cryotherapy device compared with a sham procedure in patients with chronic rhinitis.

Primary endpoint:

The percentage of responders at 90 days. Responders are defined as participants with a 30% or greater reduction in rTNSS relative to baseline. The active treatment group will be compared with the sham-control group.

Secondary endpoints:

The following secondary endpoints will compare the active treatment group with the sham-control group at 30-day and 90-day follow-ups:

- The mean change from baseline in rTNSS score.
- The mean change from baseline in Standardized Rhinoconjunctivitis
 Quality of Life Questionnaire (RQLQ(S)) score.

- Mean change from baseline in EuroQol 5-dimension survey (EQ-5D-5L) scores.
- Percent of patient satisfaction at follow-up.
- The rate of serious device- and/or procedure-related adverse events.

The following secondary endpoints will be assessed at all follow-ups for all participants who receive active treatment (randomized or crossover):

- The percentage of responders
- The mean change from baseline in rTNSS score
- The mean change from baseline in RQLQ(S) score
- Mean change from baseline in EQ-5D-5L scores
- Percent of patient satisfaction at follow-up

Additional exploratory outcomes will be detailed in the Statistical Analysis Plan.

Study assessments

- Screening
- Baseline
- Randomization and procedure
- 30-Day postprocedure follow-up
- 90-Day postprocedure follow-up (unblinding of initial treatment)
- 180-Day postprocedure follow-up
- 270-Day postprocedure follow-up
- 365-Day postprocedure follow-up

Additionally, sham-control participants will be offered the option to receive active treatment after the 90-day follow-up. Those choosing to do so who continue to meet the eligibility criteria will then complete all the study assessments starting with the new active procedure. Follow-up visits beyond 90 days are only for participants treated with ClariFix (randomized or crossover).

Sponsor:

Stryker ENT, [name] USA

Data management and monitoring:

Stryker ENT, [name] USA

Abbreviations and Acronyms

AE Adverse event

CFR Code of Federal Regulations (US)

CI Confidence interval

eCRF Electronic case report form EDC Electronic data collection

EQ-5D-5L EuroQol-5-dimension survey (5 level) FDA Food and Drug Administration (US)

GCP Good Clinical Practice

HIPAA Health Insurance Portability and Accountability Act of 1996 (US)

IB Ipratropium bromide (Atrovent)

ICF Informed Consent Form IFU Instructions for use

IRB Institutional Review Board

NOSE Nasal Obstruction Symptom Evaluation scale

PRO Patient-reported outcome

RQLQ(S) Standardized Rhinoconjunctivitis Quality of Life Questionnaire

rTNSS Reflective Total Nasal Symptoms Score

SAE Serious adverse event
US United States of America
VAS Visual analog scale

Table of Contents

Investigator	Signature Page	ii
	ct Information	
Study Spc	nsor:	iii
Study Cor	ntact:	iii
Investigation	nal Plan Summary	iii
Abbreviation	ns and Acronyms	vi
1 Backgre	ound and Purpose	3
1.1 Bac	ckground	3
1.2 Rep	port of prior investigations	4
1.3 Pur	pose	4
2 Protoco	.1	4
	dy design	4
2.2 Stu	dy objective	
2.2.1	Primary objective	5
2.2.2	Secondary objectives	5
2.3 Stu	dy endpoints	
2.3.1	Primary endpoint	6
2.3.2	Secondary endpoints	
2.3.3	Exploratory endpoints	
	dy size and duration	
	dy hypothesis	
	mple size estimation	
	ta analyses	
	Missing data	
	dy population	
2.8.1	Inclusion criteria	
2.8.2	Exclusion criteria	
	ncomitant medications	
2.9.1	Prohibited medications	
	thods and procedures	
2.10.1	Eligibility assessment	
2.10.2	Screening visit	
	Baseline	
2.10.4	Randomization and blinding	
2.10.5	Procedure (Active and Sham)	
2.10.6	30-Day and 90-day follow-up visits	
2.10.7	180-Day, 270-day, and 365-day follow-up visits	
2.10.8	Early withdrawal and lost to follow-up	
2.10.9	End of study	
	dy assessments and data collection	
2.11.1	Primary endpoint assessments	
2.11.2	Secondary endpoint assessments	
2.11.3	Additional assessments	
	enefit Analysis	

1.1 Background

Rhinitis is a very common condition throughout the world. In the Unites States (US) alone, it affects 10-30% of the adult general population (30-60 million people). The prevalence has been increasing in recent decades, making it the 5th most common chronic disease in the US. Rhinitis is the inflammation of the nasal mucosa affecting patients with at least 1 of the following symptoms: nasal congestion, rhinorrhea, sneezing, and nasal itching.

The current standard of care to control rhinitis starts with pharmacologic interventions. Over the counter nasal steroids (ie, Flonase, Nasonex) and oral antihistamines (ie, Claritin, Allegra, Zyrtec) are the mainstays of medical management. The disadvantages of these medications are that they require daily use and have limited effectiveness, especially against nonallergic rhinitis. Sedating antihistamines such as Benadryl are used intermittently but the somnolent side effects are not usually well tolerated.

Prescription medications are used when over the counter medication management fails. Oral steroids can be effective in the short term but carry more severe long-term side effects, including immunosuppression, osteoporosis, Cushing syndrome, and diabetes. Adrenergic agents such as Afrin are effective but quickly result in tolerance and "rebound" (recurrence and sometimes worsening of symptoms when off the medication).

Surgical treatments are performed when pharmacological treatments do not provide an adequate response. These treatments include electrocautery, chemocautery, laser cautery, microdebrider turbinoplasty, radiofrequency ablation, subtotal turbinectomy, total inferior turbinectomy, and submucosal resection. These procedures primarily seek to address the nasal obstructive component through reduction of the inferior turbinate.

A variety of cryosurgical tools for destruction of tissue in the nasal passageway to treat nasal obstruction or symptoms of rhinitis have been reported in the literature. ^{1,2,3,4,5,6,7,8,9,10,11} Target nasal passageway locations for cryosurgery have included the nasal soft tissue that covers the turbinates and includes nasal nerves. All of the studies have included patient-reported outcomes (PRO) of nasal symptoms, which is a commonly accepted method for demonstrating the effectiveness outcomes in the nasal passageway. Physicians also performed visual assessments of nasal congestion and recorded the presence of complications including resolution of any adverse symptoms. Although published reports reflect improvement in symptoms and a low rate of complications, endoscopic cryotherapy techniques and tools have not been fully optimized to achieve consistent outcomes.

Arrinex, Inc. (now part of Stryker ENT) has developed a novel cryotherapy device, the ClariFix Cryotherapy device, designed specifically to facilitate a transnasal approach to allow cryoablation of unwanted tissue in the nasal passageway.

1.2 Report of prior investigations

A pilot clinical study was performed at 3 investigational sites in the US to evaluate the performance of the ClariFix device as a cryosurgical tool to treat patients with chronic rhinitis. This study was a prospective, multicenter, single-arm interventional, nonsignificant risk study of the ClariFix device.

A total of 27 participants were enrolled and bilateral treatments were successfully completed with no complications in 100% of participants using injected or topical anesthesia in the office. All participants completed the 30-day follow-up and 24 of the 27 participants (88.9%) completed the 90-day follow up (3 participants were lost-to-follow-up) and participated in the extended follow-up. Nasal symptoms, assessed by the reflective Total Nasal Symptom Scale (rTNSS), were significantly reduced at each follow-up interval compared with baseline. The average rTNSS score was reduced by 58% from 6.2 at baseline to 2.6 at 30 days and the reduction was maintained at 2.7 at 90 days (56% reduction). Extended follow-up showed sustained improvements: average rTNSS of 2.3 at 180 days post treatment. Eighty-one percent (22/27) of participants had at least a 1-point improvement of rTNSS scores at 30 days and 79% (19/24) of participants had improved rTNSS scores at 90 days. The visual analog scale (VAS) scores similarly demonstrated significant reductions in nasal symptoms. The average total VAS score was reduced by 50% and 53% at 30 and 90 days, respectively. There were no device- or procedure-related serious adverse events (SAEs) reported during the study. This pilot study demonstrated that office-based treatment using the ClariFix device was safe, well-tolerated, and effective in reducing nasal symptoms in participants with chronic rhinitis.

1.3 Purpose

This study will build on previous results and is designed to demonstrate the superiority of treatment with the ClariFix cryotherapy device compared with a sham procedure in patients with chronic rhinitis.

2 Protocol

2.1 Study design

This is a prospective, multicenter, randomized, sham-controlled, single-blinded study. Eligible participants will be randomized 1:1 to active treatment or sham-control. Participants will be blinded to their treatment assignment until the 90-day follow-up visit, at which time, the participants will be informed of their treatment and sham-control participants will be offered the opportunity to crossover to active treatment if they still meet the inclusion and exclusion criteria. Active treatment participants and crossover control participants will be followed through 365 days after the procedure.

[figure not shown]

Figure 1 presents the study design and participant flow.

Figure 1. Study Design and Participant Flow

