2.3 Study endpoints

2.3.1 Primary endpoint

The primary endpoint is the percentage of responders at 90 days. Responders are defined as participants with a 30% or greater reduction in rTNSS relative to baseline. The active treatment group will be compared with the sham-control group.

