2.4 Study size and duration

The study will be conducted at up to 12 investigational centers in the US.

A sufficient number of participants will be screened and consented to reach a total enrollment of 128 participants. Enrollment in the study is anticipated to take approximately 12 months. Participants are considered enrolled at the time of randomization and procedure.

The expected duration of study participation is 13 months for active treatment participants and 16 months for sham-control participants who chose to crossover to active treatment. There is a maximum of a 30-day screening period for all participants. Postprocedure follow-up for active treatment participants is 365 days (12 months). Sham-control participants who meet the criteria may crossover to active treatment after their 90-day follow-up and then complete the same full 365-day postprocedure follow-up as the active participants. Those sham-control participants who

do not meet the original inclusion/exclusion criteria at the 90-day follow-up or elect not to crossover to the active treatment will be exited from the study after their 90-day follow-up.

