2.8.1 Inclusion criteria

Study participants MUST meet all of the following criteria:

- 1. Be \geq 21 years of age.
- 2. Has been diagnosed with chronic nonallergic or allergic rhinitis.
- 3. Have moderate to severe symptoms of rhinorrhea (individual rTNSS symptom rating of 2 or 3), mild to severe symptoms of nasal congestion (individual rTNSS symptom rating of 1, 2, or 3), and a minimum total rTNSS score of 4 (out of 12) at baseline.
- 4. Have an allergy test (by skin prick or intradermal testing or by validated *in vitro* tests for specific Immunoglobin E [IgE]) on file within 12 months of the baseline visit.
- 5. Be an appropriate candidate for bilateral ClariFix treatment performed under local anesthesia.
- 6. Be willing and able to comply with all study elements, as indicated by their written informed consent.

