2.10.4 Randomization and blinding

Randomization assignments will be generated by in independent statistician using variable block size distribution by site with a 1:1 allocation to active or sham treatment. Randomization will also be stratified by allergy subgroup (allergic, nonallergic). The randomization schedule will be entered into the Medrio electronic data collection (EDC) randomization module. Randomization will occur on the day of the procedure and after all baseline data have been collected and eligibility has been confirmed. All randomized and treated participants will be considered enrolled. Confirmation of randomization assignment from EDC will be printed and filed in the study record.

This is a single-blind study; participants will be blinded to the randomized assignment. To facilitate blinding, control participants will undergo a sham procedure using the ClariFix device without a cryogen cannister. To support blinding, participants will wear blindfolds during the procedure to limit any visual clues that may suggest the treatment assignment. A separate device with a canister held near the participant will be used to provide the sound of the gas release from the cannister. A standardized script for the physician/staff will be used during the procedure to assure blinding. Additionally, local anesthesia regimes will be the same for both treatment groups within each investigational center.

Participants will complete a blinding questionnaire at completion of the procedure and at the 30-day and 90-day follow-up visits to assess the adequacy of the blinding procedures. Upon

completion of their 90-day visit, each participant will be unblinded. Sham control participants will be offered the opportunity to receive active treatment if they wish and still meet eligibility criteria.

Before the 90-day visit, unblinding of participants will only occur when medically necessary. In the event of a device-or procedure-related SAE, the sponsor may authorize the site to unblind the participant in order to adequately assess the event.

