2.10.5 Procedure (Active and Sham)

Pregnancy testing

Before the procedure, urine pregnancy tests are required for all women of childbearing potential. In the case of pregnancy, use medical judgement to select appropriate procedural anesthesia medications (eg, low doses of epinephrine and lidocaine) that are safe for use during pregnancy.

Procedure anesthesia

The local anesthesia regimen for the procedure for both active and sham treatments will be performed according to the physician's usual practice. Information regarding the anesthesia regimen will be documented in the study records.

Study procedure

Below is a high-level description of the procedure for both the active and sham procedures. Detailed instructions on the preparation, usage, and storage of the ClariFix device is available in the instructions for use (packaged with the device). To maintain the participant blind during the procedure, the sham devices will be identical to the active devices except the cryogen cannister will not be inserted into the device.

- 1) Review and update concomitant medications.
- 2) Perform quantitative endoscopic rhinoscopy before administration of nasal decongestant to evaluate nasal congestion.
- 3) Administer decongestant. If the participant is a woman of childbearing potential, use medical judgement to select a decongestant (eg, oxymetazoline) that is safe to use during pregnancy.
- 4) Perform quantitative endoscopic rhinoscopy to assess degree/extent of rhinorrhea and postdecongestant nasal congestion, and plan target treatment placement at the middle meatus.
- 5) Administer local anesthesia to both sides of the nasal cavity.
- 6) Have the participant put on the blindfold.
- 7) Prepare the ClariFix device according to the IFU (for sham treatment, do not insert the cryogen cannister).
- 8) Place the cryoprobe in firm contact with the targeted middle meatus tissue under visual guidance.

- 9) For active treatment: initiate the flow of cryogen for a total of 30 seconds and, using endoscopic visualization, ensure the cryoprobe is functioning.

 For sham treatment: turn on the device and leave the cryoprobe in contact with tissue for the 30 seconds, tissue will not freeze with the sham treatment. Use a separate device held near the participant to provide the sound of gas release from the cannister.

 For both treatments, during this time, instruct the participant breathe in and out through their mouth.

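### The 90-day rTNSS decides the primary endpoint and, as written, also gates crossover to active treatment, which can bias the comparison if suspicion of sham differs by arm

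*Combined protocol and SAP*

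**What the plan says.** - **Gate.** Section 2.1 offers crossover on a condition: "sham-control participants will be offered the opportunity to crossover to active treatment if they still meet the inclusion and exclusion criteria". Sections 2.4 and 2.10.4 and the Investigational Plan Summary repeat it. Section 2.4 adds the timing: sham participants who "do not meet the original inclusion/exclusion criteria at the 90-day follow-up" leave the study.
- **Symptom criterion.** Inclusion criterion 3 (section 2.8.1) requires a rhinorrhea rating of 2 or 3, a congestion rating of 1 to 3, "and a minimum total rTNSS score of 4 (out of 12) at baseline".
- **Primary endpoint.** Section 2.3.1, assessed at 90 days: "Responders are defined as participants with a 30% or greater reduction in rTNSS relative to baseline".
- **After crossover.** The Investigational Plan Summary says crossover participants "will then complete all the study assessments starting with the new active procedure". In Table 2 the crossover footnote is attached to the procedure and later columns, not to screening or baseline, and the procedure column contains no rTNSS.
- **Blinding.** Under section 2.10.4, unblinding comes after scoring: upon "completion of their 90-day visit, each participant will be unblinded". A blindfold, a separate source of gas sound, a script and the same anesthesia regimen within each center support the blind. A blinding questionnaire is completed after the procedure and at 30 and 90 days. No use of the answers in the primary analysis is described.

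**The concern.** The primary outcome is entirely patient-reported. If the same answers also settle whether a sham participant may receive active treatment, a participant who believes they had sham has something to gain from reporting persistent symptoms. Suspicion could plausibly differ between arms, since section 2.10.5 notes that "tissue will not freeze with the sham treatment" and section 3.2 lists effects of cold such as crusting, facial pain and numbness. If over-reporting is then commoner in the sham arm, the sham responder rate falls for reasons unrelated to treatment, and the superiority test in section 2.5 rejects too often when there is no effect.

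**Working it through.** **1. The plan's own figure.** Section 2.6 gives 73.5% and 45% responders, one-sided alpha 0.025, 90% power and 1:1 allocation. Section 2.5 gives a Z-test of two proportions. With pooled variance, mean rate p̄ = (0.735 + 0.45)/2 = 0.5925:

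n per arm = [1.96 × √(2 × 0.5925 × 0.4075) + 1.2816 × √(0.735 × 0.265 + 0.45 × 0.55)]² / 0.285² = 60.4, rounded up to 61.

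This matches the stated 61 per arm (122 in total). The sample size is not at issue; it supplies the setting for the checks below.

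**2. How far gate and endpoint overlap.** A responder has a 90-day total of at most 0.7 × baseline. The gate needs a total of at least 4.

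| Baseline total | Responder if 90-day total is at most | Totals that are response and also meet the total-score rule |
|---|---|---|
| 4 | 2 | none |
| 5 | 3 | none |
| 6 | 4 | 4 |
| 7 | 4 | 4 |
| 8 | 5 | 4–5 |
| 9 | 6 | 4–6 |
| 10 | 7 | 4–7 |
| 11 | 7 | 4–7 |
| 12 | 8 | 4–8 |

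At baseline 4 or 5, any total that keeps eligibility is non-response. At 6 or 7 only a score of exactly 4 is both. The mean baseline in the pilot study (section 1.2) was 6.2, so the tight end of the table is relevant. The rhinorrhea and congestion minimums can only narrow the overlap.

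**3. Effect on the false-positive rate.** Let q be the fraction of would-be responders who over-report into non-response. The documents give no value, so q is an assumption shown as a range. The observed responder rate in an arm is p × (1 − q). Under no true effect, p = 45% in both arms. The rejection probability comes from exact binomial enumeration of the pooled one-sided Z-test, 61 per arm, critical value 1.96.

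| q active | q sham | Observed rates, active vs sham | False difference (points) | P(reject) |
|---|---|---|---|---|
| 0 | 0 | 45% vs 45% | 0 | 2.8% |
| 0 | 5% | 45% vs 42.75% | 2.25 | 4.8% |
| 0 | 10% | 45% vs 40.5% | 4.5 | 7.7% |
| 0 | 20% | 45% vs 36% | 9.0 | 17.7% |
| 10% | 20% | 40.5% vs 36% | 4.5 | about 7.5% |

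The first row is 2.8% rather than 2.5% because the test is approximate at this sample size. A normal approximation gives 2.5%, 4.4%, 7.2% and 17.1% for the first four rows, the same pattern.

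**4. Equal over-reporting.** With q = 10% in both arms and no true effect, the false difference is 0. At the planned rates the observed rates become 0.735 × 0.9 = 66.15% and 0.45 × 0.9 = 40.5%. The difference shrinks from 28.5 to 25.65 points, and exact power falls from about 91% to 83%.

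**5. Break-even at the planned rates.** The observed difference widens only if 0.45 × q(sham) exceeds 0.735 × q(active), that is, if q(sham) is more than 0.735/0.45 = 1.63 times q(active).

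**The case against.** The strongest reply is that the 90-day score is given under blind, with several measures to protect that blind, and that nothing in the documents shows suspicion will differ between arms. Active participants who suspect sham face the same incentive. Section 2.10.5 also allows retreatment or other surgery after the 90-day visit for continuing or recurrent symptoms, which gives participants who believe they had active treatment some reason to report persistence too. From baseline 6 upward a participant can meet the total-score rule and still be a responder, and anyone whose symptoms truly persist qualifies without exaggerating. Criterion 3 is worded for the baseline visit, so its application at day 90 is read from section 2.4 rather than spelled out.

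All of this stands, and it limits the size and certainty of the problem. It does not remove the dual use: section 2.4 places the check at the 90-day follow-up, and no other current score is scheduled. Suspicion is enough to create the incentive; knowledge of assignment is not needed.

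Three stronger readings are tempting but unsupported:

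- **That the design necessarily biases toward the device.** It does so under the null only if over-reporting is more frequent in sham, which the documents do not establish.
- **That the crossover is free of charge, or that participants know the cut-off.** The documents say neither. Consent pages are not available, so what participants are told cannot be judged.
- **That the crossover baseline is inflated.** No section says the 90-day score is the baseline for crossover participants; the original baseline is an equally possible reading. What can be said is that the crossover baseline is not named.

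**Conclusion.** The concern holds in a conditional form. As written, one self-reported score is both the primary outcome and part of the gate to active treatment, and this creates an avoidable incentive to score high. The direction of any bias depends on whether suspicion and over-reporting differ by arm.

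On the assumed fractions of 5% to 20% in sham only, the false-positive rate would be 4.8% to 17.7% instead of 2.8%; with 20% in sham and 10% in active it would be about 7.5%. These figures show sensitivity and are not predictions. They rest on a 45% null responder rate, 61 evaluable per arm, and over-reporting large enough to change responder status, which is easiest at low baseline totals. The change is worth making because it is cheap and protects the primary comparison.

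**What to change.** 1. State in sections 2.1, 2.4 and 2.10.4 that the 90-day rTNSS does not determine crossover eligibility, and make sure participants are told this.
2. Apply the existing criteria, unchanged, to a separate questionnaire set completed after the 90-day questionnaires are locked and before the crossover procedure.
3. Name the baseline for crossover participants' change scores and responder status. A score taken after unblinding is itself open to inflation, so it should not be the only reference. Report crossover results separately from randomized active participants, and also relative to the original baseline, before the pooling planned in section 2.7.
4. Pre-specify a sensitivity analysis of the primary endpoint by the blinding-questionnaire guess already collected. Include the guess given just after the procedure, since later guesses may themselves reflect symptom response.

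**Cost.** A short amendment, a sentence for participants, and one extra questionnaire set with an eligibility check for at most about 64 people (half of 128). The remaining downside is that the crossover score is not blinded, which is why item 3 is needed.
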